4.3 Study Enrollment Procedures

4.3.1 Prior to implementation of this protocol, sites must have the protocol and the protocol consent form approved by their local institutional review board (IRB).

Once a candidate for study entry has been identified, details will be carefully discussed with the subject. The subject will be asked to read and sign the approved protocol consent form.

Candidates for study entry will be identified using an existing IRB-approved data repository of HIV-infected persons in the Northwestern Medicine Enterprise Data Warehouse (NMEDW). These candidates will be identified by querying this NMEDW data repository for any living HIV-infected persons aged 18 to 75 who have no HIV viral RNA values of 400 copies/ml or greater anytime in the previous 12 months from the time of screening and who have any diagnosis of coronary heart disease (CHD) based on any documented ICD-9-CM codes 410-414 and/or ICD-10-CM codes I21-I25. Candidates will also be identified by calculating the 10-year ASCVD risk of patients referred by primary care providers. Once these candidates are identified, participants will be excluded if they are noted to be prescribed atorvastatin 20mg daily or greater, rosuvastatin 10mg daily greater, atazanavir/ritonavir (at any dose), lopinavir/ritonavir (at any dose), simeprevir.(at any dose), or are not currently taking antiretroviral therapy. Of the remaining candidates, persons with an active primary care provider and/or infectious disease provider at Northwestern Medicine will be eligible to be contacted for enrollment via telephone. The order of contacting patients will be by those with the most recent new diagnoses of CHD first, with the plan to continue contacting patients (those with the earlier CHD diagnosis dates would be contacted later, then patients with no known CHD but with 10-year ASCVD risk of 15% or greater) until the target enrollment is achieved.

4.3.2 Randomization

Subjects who meet enrollment criteria will be randomized at Week 2 (the end of the pravastatin 40ml daily run-in period) in a 1:1 ratio according to the study treatment that has been randomly assigned to the Patient Number on the Randomization List held by the local site pharmacist.

Randomization will be stratified by type of ART: patients taking any booster (ritonavir or cobicistat) as part of their ART regimen and patients not taking a booster.

5.0 STUDY TREATMENT

5.1 Regimens, Administration, and Duration

After a 2-week pravastatin 40mg daily run-in period, subjects will be randomly assigned to rosuvastatin 20mg daily or pravastatin 40mg daily at week 2 in a 1:1 ratio. At week 6, subjects on the Rosuvastatin arm may have their dose escalated to 40mg daily.

Run-in: Pravastatin 40mg daily for 2 weeks (Weeks 0-2)

Randomization (1:1 ratio) at Week 2:

- Moderate intensity strategy: Pravastatin 40mg once daily for 12 weeks (Weeks 2-14)
OR
- High-intensity strategy: Rosuvastatin 20mg once daily for 4 weeks (Weeks 2 to 6)
 - Continue Rosuvastatin 20 mg once daily (Weeks 6 to 14) if:
 - AST or ALT between 1.5x and 3x ULN
OR
 - CK between 3x and 10x ULN
OR
 - Grade 1 or 2 toxicity attributable to rosuvastatin is present
 - Escalation of Rosuvastatin to 40 mg daily (Weeks 6 to 14) if:
 - AST, ALT, and CK \leq 1.5x ULN at week 6
AND
 - CK \leq 3x ULN at week 6
AND
 - No grade 1 or greater toxicity attributable to rosuvastatin is present

5.1.1 Regimen

Subjects should begin study treatment within 72 hours after entry and continue on study treatment for 14 weeks.

Study drugs will be supplied in bottles for this open-label study. The pharmacist will dispense 2 weeks (15 tablets) of pravastatin 40 mg at week 0 to all participants. At week 2, subjects will be randomized to receive either 12 weeks (3 bottles, 90 tablets) of rosuvastatin 20 mg tablets or 12 weeks (85 tablets) of pravastatin 40 mg tablets.

Based on LFTs, CK, and safety/toxicity assessments at Week 6, participants in the rosuvastatin arm will be notified within 5 days whether or not they are to escalate to two 20mg tablets daily or continue taking one tablet daily. If the dose is escalated, participants will need to return to the pharmacy within the next 4 weeks to receive an additional supply of 30 tablets (1 bottle) of rosuvastatin 20mg.

At the Week 14 visit, subjects should return any remaining study-provided study products.

5.1.2 Administration

Pravastatin will be administered orally as one 40 mg tablet once daily with or without food.

Rosuvastatin will be administered orally as one or two (high-dose) 20 mg tablet(s) once daily with or without food.

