5.3.2 Study Product Accountability

The site pharmacist is required to maintain complete records of all study products received. All unused study products must be returned to the site (or as otherwise directed by the sponsor) after the study is completed or terminated.

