5.5 Adherence Assessment

Adherence to all study drugs will be monitored by self-report.

Subjects will be asked to keep a patient diary noting the day and date they take their study drug and any adverse events. They will be asked to bring their patient diary to each study visit along with all used and unused study drug containers.

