6.3.4 Clinical Assessments

Complete Physical Exam

A complete physical examination performed at any time between screening and the entry evaluation is to include at a minimum an examination of the skin, head, mouth, and neck; auscultation of the chest; cardiac exam; abdominal exam; and examination of the lower extremities for edema. The complete physical exam will also include signs

and symptoms, diagnoses, height, weight, and vital signs (temperature, pulse, respiration rate, and blood pressure).

Targeted Physical Exam

A targeted physical examination is to be performed after screening and will be driven by any previously identified or new signs or symptoms including diagnoses that the subject has experienced since the last visit. This examination includes vital signs (temperature, pulse, respiration rate, and blood pressure).

Signs and Symptoms

At entry, record on the CRFs all signs/symptoms occurring within 30 days prior to entry.

After entry, record all Grade ≥ 1 signs/symptoms, any signs/symptoms regardless of grade that lead to a change in treatment, or that meet EAE, SAE, or ICH guidelines.

Diagnoses

At screening, record diagnoses in the medical history per section 6.3.2. At study entry and thereafter, record all new diagnoses since the last study visit identified by the ACTG criteria for clinical events and other diseases.

Concomitant Medications

Record any prescription medications taken since the last study visit, including actual or estimated start dates and stop dates in the CRF. Current non-prescription, alternative and traditional medications are recorded in the source documents and CRFs.

Study Treatment

Record all study treatment modifications, including initial doses, subject-initiated and/or protocol-mandated modifications, and inadvertent and deliberate interruptions of more than 1 day since last visit. Record any permanent discontinuation of treatment.

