6.3.7 Adherence Assessment

Adherence to all study medications will be assessed by self-report. Sites will provide adherence reinforcement, according to local standard practice throughout the study. Subjects with poor adherence will be provided counseling by the site.

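### Self-report and a day-and-date diary cannot tell one 20 mg rosuvastatin tablet from two, so the exposure behind the 40 mg results would be uncertain

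*Combined protocol and SAP*

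**What the plan says.** The dose form is set in section 5.1.2: "Rosuvastatin will be administered orally as one or two (high-dose) 20 mg tablet(s) once daily with or without food". Under section 5.1.1, a patient in the rosuvastatin arm receives 90 tablets of 20 mg at week 2. Within 5 days of the week 6 assessments the patient is told whether to move to two tablets daily. If so, one further bottle of 30 is collected.

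On adherence, section 5.5 says "Adherence to all study drugs will be monitored by self-report", and section 6.3.7 repeats it: "Adherence to all study medications will be assessed by self-report". The diary is described this way: "Subjects will be asked to keep a patient diary noting the day and date they take their study drug and any adverse events".

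Other information on dosing is collected:

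- Containers (5.5): "They will be asked to bring their patient diary to each study visit along with all used and unused study drug containers".
- Leftover product (5.1.1): "At the Week 14 visit, subjects should return any remaining study-provided study products". Section 5.3.2 adds: "All unused study products must be returned to the site (or as otherwise directed by the sponsor) after the study is completed or terminated".
- Dose changes on the CRF (6.3.4): "Record all study treatment modifications, including initial doses, subject-initiated and/or protocol-mandated modifications, and inadvertent and deliberate interruptions of more than 1 day since last visit".
- Plasma statin concentrations about 12 hours after dosing at weeks 2, 6 and 14 (6.3.8).

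No section asks for a tablet count, defines adherence numerically, or says how containers or drug levels bear on it.

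**The concern.** An escalated patient who keeps taking one tablet writes the same diary line as one who takes two. The CRF entry for subject-initiated changes catches this only if the patient reports it.

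The stake is exposure. Section 2.0 calls the trial a pilot for studies adequately powered for safety, and section 2.1 says rosuvastatin 20-40 mg has not been evaluated in this population. If some escalated patients took 20 mg, the adverse-event record and LDL-c response after escalation would describe a lower dose than the one assigned.

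The drug-level endpoint in section 9.2.2, levels above 400% of the expected steady state, is also affected, because the expected level depends on the dose taken. Assuming levels proportional to dose, a patient taking 20 mg but judged against 40 mg has the ratio halved, so a true 400% reads as 200%.

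**Working it through.** **Plan's own figure.** Section 9.4: difference 25 mg/dl, SD 20, two-sided alpha 0.05, power 0.80. n = 2 × [20 × (1.960 + 0.842) / 25]² = 10.05, rounded up to 11 per arm, which agrees with the plan. (A t-based solution gives 11.09, that is 12.) The point does not depend on this figure; it is used only in the last step.

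**Can a count separate the two patterns?** Inputs are from section 5.1.1. Weeks 2-14 are 84 days, of which weeks 2-6 are 28 and weeks 6-14 are 56.

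- Two daily from the week 6 day: 28 + 2 × 56 = 140 tablets.
- Two daily after the full 5-day notice: 33 + 2 × 51 = 135 tablets.
- One daily throughout: 84 tablets.
- Supply: 90 + 30 = 120 tablets.

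At week 14 the one-tablet patient has 120 − 84 = 36 left, or 90 − 84 = 6 if the extra bottle was never collected. The two-tablet patient has none left and is 15 to 20 tablets short.

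At week 10 the first 90 tablets alone are enough. The two-tablet patient has used 28 + 56 = 84 (6 left), or 33 + 2 × 23 = 79 with the full notice (11 left). The one-tablet patient has used 56 (34 left). A count separates them; the diary as described does not.

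**What the supply does to a simple ratio.** After 28 tablets in weeks 2-6, 120 − 28 = 92 remain for weeks 6-14. Tablets due are 112, or 5 + 102 = 107 with the full notice. A fully compliant escalated patient could score at most 92/112 = 82%, or 92/107 = 86%. The schedule in section 6.1 also lists dispensing at weeks 6 and 10 without quantities, so 120 is what section 5.1.1 provides, not necessarily what is handed out.

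**LDL-c cost of one tablet instead of two.** Section 9.4 predicts reductions of 55-60% at 20 mg, 60-63% at 40 mg and 30% on pravastatin 40 mg. Relative to the pravastatin level (0.70 of untreated):

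- 20 mg: 1 − 0.45/0.70 = 35.7% to 1 − 0.40/0.70 = 42.9%; midpoint 39.3%.
- 40 mg: 1 − 0.40/0.70 = 42.9% to 1 − 0.37/0.70 = 47.1%; midpoint 45.0%.
- Difference: 42.9 − 42.9 = 0 to 47.1 − 35.7 = 11.4 points; 5.7 at the midpoints.

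**Effect on the primary comparison (illustrative).** Assume every rosuvastatin patient is escalated and takes one tablet, and that the untreated-scale gap between doses (60 − 60 = 0 to 63 − 55 = 8 points; 61.5 − 57.5 = 4 at the midpoints) applies to the expected mean LDL-c of 105 mg/dl. The 25 mg/dl difference becomes 25 − 4.2 = 20.8 (range 25 − 8.4 = 16.6 to 25). At 20 per arm, power by the normal approximation is about 0.91 (range 0.75 to 0.98). At 15 per arm, the enrolment goal of 30 in section 9.4, it is 0.81 (0.62 to 0.93).

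**The case against.** The strongest reply is that the plan collects more than a diary. Dose changes go on the CRF, adherence is assessed at every visit from week 2, and the schedule has a week 10 phone call specific to escalated patients. Drug levels at week 6 on 20 mg and at week 14 after escalation give a within-patient check. That stands in part. But the CRF entry and the call rely on the patient's account. The week 14 level is a single 12-hour sample that cannot describe eight weeks of dosing, and no rule ties it to adherence. It also feeds a secondary endpoint, so inferring the dose from it and then judging it against that dose would be circular.

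A second reply is that a tablet count fails on the plan's own supply. This stands against a ratio with a fixed denominator, as the 82% and 86% ceilings show. It does not stand against a count as such, since the week 10 count is readable from the first 90 tablets.

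A reader might go further in four ways that the documents do not support:

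- That a one-tablet patient would be classed as fully adherent at 40 mg. The plan has no adherence definition, threshold or adherence-based analysis.
- That the primary result is compromised. Section 9.6.1 is intention-to-treat, and section 9.2.1 compares a strategy of 20 mg uptitrated to 40 mg, not 40 mg alone.
- That 40 mg is the only untested dose. Section 2.1 says the same of 20 mg.
- That self-report in this open-label trial must err towards full adherence. That may be so, but nothing in the documents shows it.

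**Conclusion.** The point holds as a limit on what can be said about exposure. The stated adherence measure cannot distinguish one tablet daily from two, and the material that could do so is collected but not used. The intention-to-treat comparison of strategies is unaffected in validity, and the power figures above are a worst case.

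The cost per affected patient is about 0 to 11 points of LDL-c reduction relative to the pravastatin level (about 6 at the midpoints), together with half the assumed exposure in the safety and drug-level results. This rests on the plan's predicted reductions and, for drug levels, on assumed dose proportionality. How many patients would be affected cannot be stated: the documents give no non-adherence rate, and sections 5.1 and 9.1 describe different conditions for escalation.

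This is worth correcting because the trial is a pilot for later safety studies and the correction is cheap. It is not a flaw that stops the trial from answering its primary question.

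**What to change.** 1. Reconcile sections 5.1, 5.1.1 and 6.1 on rosuvastatin supply: 120 tablets provided against 135 to 140 for two daily from week 6, with dispensing at weeks 6 and 10 scheduled without quantities.
2. In section 5.5, add the number of tablets taken to each diary line.
3. In sections 5.5 and 6.3.7, make a tablet count the adherence measure for weeks 0-2, 2-6, 6-10 and 10-14, using the containers already brought to each visit: tablets on hand at the start, plus tablets dispensed, minus tablets on hand at the end, divided by tablets due. Take tablets due from the actual visit and escalation dates, capped at the tablets available to the patient, so that a supply shortage is not counted as non-adherence. Keep self-report as supportive.
4. Report the count by arm. For escalated patients, report the proportion consistent with two tablets daily, read alongside the week 6 and week 14 drug levels.
5. Leave the intention-to-treat primary analysis unchanged.

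The cost is a wording change, one diary column, a few minutes of counting per visit and one descriptive table. The downside is that lost or dumped tablets look like tablets taken, so a count is an upper bound on intake.

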5.2 Study Product Formulation and Preparation

5.2.1 Pravastatin sodium 40 mg tablets. Store at 25°C (77°F); excursions permitted to 15°C - 30°C (59°-86°F). Each bottle contains 100 tablets.

Rosuvastatin 20 mg tablets. Store at 25C (77F); excursions permitted to 15 to 30C (59 to 86F). Each bottle contains 30 tablets.

The study drug will be stored by the study site at controlled room temperature, 15 to 30°C (59 to 86°F). Subjects will be instructed to store the medication in original packaging at room temperature according to the instructions outlined on the Drug Administration Instructions.

5.3 Pharmacy: Product Supply, Distribution, and Accountability

5.3.1 Study Product Supply/Distribution

The drug products used will be rosuvastatin 20 mg oral tablets (AstraZeneca: London, UK) and pravastatin 40 mg oral tablets (Bristol-Meyers Squibb: New York, NY, USA).

These are approved drugs in regular clinical use at the doses proposed in this study and will be purchased through the Northwestern Memorial Hospital Investigational Pharmacy.

5.3.2 Study Product Accountability

The site pharmacist is required to maintain complete records of all study products received. All unused study products must be returned to the site (or as otherwise directed by the sponsor) after the study is completed or terminated.

5.4 Concomitant Medications

Below are lists of selected concomitant medications. These lists are only current as of the date of this protocol. Therefore, whenever a concomitant medication or study agent is initiated or a dose changed, investigators must review the concomitant medications' and study agents' most recent package inserts, and Investigator's Brochures to obtain the most current information on drug interactions, contraindications, and precautions.

5.4.1 Required Medications:

All subjects should be maintained on the same antiretroviral medications throughout the entire study period, as medically feasible, with no introduction of new chronic therapies.

Standard therapy for HIV and care in the setting of CHD and/or high risk for ASCVD is allowed except for treatments noted in the exclusion criteria described above and as noted in the prohibited medications section below.

5.4.2 Prohibited Medications

The following medications are prohibited during the study and administration will be considered a protocol violation.

- Atazanavir/ritonavir
- Lopinavir/ritonavir (Kaletra)
- Cyclosporine
- Rifampin
- Simeprevir
- Cholestyramine / aspartame
- Cholestyramine / sucrose
- Colesevelam
- Colestipol
- Prevalite
- Questran
- Questran Light
- Welchol
- Colestid
- Ezetimibe
- Zetia
- Liptruzet
- Vytorin
- Fenofibrate
- Fenofibric acid
- Gemfibrozil
- Antara
- Lipofen
- Lofibra
- Tricor
- Fenoglide
- Triglide
- Trilipix
- Fibrincor
- Lopid
- Icosapent ethyl
- Lomitapide
- Mipomersen
- Vascepa
- Juxtapid
- Kynamro
- Niacin
- Niaspan
- Simcor
- Niacinamide
- Simvastatin

- Fluvastatin
- Lovastatin
- Cerivastatin
- Atorvastatin
- Pitavastatin
- Advicor
- Altocor
- Altoprev
- Atorlip
- Baycol
- Caduet
- Canef
- Inegy
- Lescol
- Lipex
- Lipitor
- Lipobay
- Lipostat
- Lipvas
- Mevacor
- Pitava
- Selektine
- Simcard
- Simcor
- Simlup
- Sortis
- Torvacard
- Torvast
- Totalip
- Tulip
- Vytorin
- Zocor

5.4.3 Precautionary Medications

Whenever a concomitant medication or study agent is initiated or a dose changed, investigators must review the concomitant medications' and study agents' most recent package inserts, Investigator's Brochures to obtain the most current information on drug interactions, contraindications, and precautions.

5.5 Adherence Assessment

Adherence to all study drugs will be monitored by self-report.

Subjects will be asked to keep a patient diary noting the day and date they take their study drug and any adverse events. They will be asked to bring their patient diary to each study visit along with all used and unused study drug containers.

6.0 CLINICAL AND LABORATORY EVALUATIONS

6.1 Schedule of Events

	SCREEN- ING	WEEK 0 ^a	WEEK 2 ^a	WEEK 6 ^a	WEEK 10	Week 14/ or discontinuation
Informed Consent	X	X				
Medical and Medication History (including cardiovascular risk; HIV RNA and CD4, lipids)	X					
Complete Physical Exam	X					
Targeted Physical Exam		X	X	X	X	X
Height , Weight	X				X	
Vital Signs	X	X	X	X	X	X
Chemistry Panel, Liver Function Tests	X	X	X	X	X	X
Creatine Kinase	X	X	X	X	X	X
Fasting Lipid Panel	X	X	X	X	X	X
Pregnancy Test	X	X				X
Hematology, Hemoglobin A1c		X				X
Stored Plasma/Serum/PBMCs		X	X			X
Pharmacokinetics/dynamics			X	X		X
Randomization			X			
Dispensing of Study Drug		X	X	X	(X)*	
Adherence Assessment			X	X	X	X
Concomitant Medication Review	X	X	X	X	X	X
AE Determination		X	X	X	X	X
Phone Call					(X)*	
Statin Intolerance Survey			X	X	X	X

*(X) if on escalated rosuvastatin dose (40mg daily)

6.2 Timing of Evaluations

6.2.1 Screening Evaluations

Screening evaluations must occur prior to the subject starting any study medications, treatments, or interventions.

Screening

Screening evaluations to determine eligibility must be completed within 45 days prior to study entry, unless otherwise specified.

In addition to data being collected on subjects who enroll into the study, reason(s) for screening failures will be captured on a Screening Failure form and will not be entered directly in REDCap.

6.2.2 Entry Evaluations

Entry evaluations must occur at least 24 hours after screening evaluation and be completed prior to the initiation of study medications.

6.2.3 Post-Entry Evaluations

On-Treatment Evaluations

Evaluations should occur +/- 2 days of the scheduled visit.

6.2.4 Discontinuation Evaluations

Evaluations for Registered Subjects Who Do Not Start Study Treatment

Subjects who do not begin study treatment should have screening and entry forms completed and entered in the database. Beyond the entry visit, no further evaluations are required. These subjects will be replaced.

Premature Treatment Discontinuation Evaluations

Subjects who discontinue the study medications before the end of the study (Week 14) should have the Premature Treatment Discontinuation evaluations done within 7 days after stopping study drugs. They will be encouraged to continue to attend all study visits and receive study evaluations as per section 6.1 through Week 14.

Premature Study Discontinuation Evaluations

All subjects who prematurely discontinue participation in the study should have the Premature Study Discontinuation evaluations done.

6.3 Instructions for Evaluations

All clinical and laboratory information required by this protocol must be present in the source documents.

All stated evaluations are to be recorded on the CRF and keyed into the REDCap database unless otherwise specified.

6.3.1 Documentation of HIV-1

Section 4.1.1 specifies assay requirements for HIV-1 documentation. HIV-1 documentation is not recorded on the CRF.

6.3.2 Medical History

The medical history must include all diagnoses identified by the ACTG criteria for clinical events and other diagnoses within 30 days. In addition, the following diagnoses should be reported regardless of when the diagnosis was made:

- AIDS-defining conditions
- Coronary heart disease
 - Previous ACS, which includes myocardial infarction and unstable angina
 - Angina
- Cerebrovascular disease
- Cancer (exclusive of basal/squamous cell skin cancer)
- Diabetes

Any allergies to any medications and their formulations must also be documented.

Cardiovascular risk: An assessment of general cardiovascular risk factors, smoking, alcohol use, substance use, family history of premature CVD, hormonal history will be assessed at screen. ASCVD risk will be calculated using the ACC/AHA ASCVD Risk Estimator (<http://tools.acc.org/ASCVD-Risk-estimator/>).

